1.6 Hypothesis

The purpose of this study is to explore the safety, tolerability and efficacy of CPX-351 with quizartinib in patients with FLT3 mutated AML. The investigators hypothesize:

The combination of liposomal nanomolar cytarabine:daunorubicin (CPX-351) with quizartinib, a second-generation FLT3 inhibitor, will be safe, tolerable and enhance the tumor response in patients with FLT3-mutated AML who have relapsed or whose tumor did not respond to standard and other therapeutic regimens.

2. STUDY OBJECTIVES

2.1 Primary Objectives

The primary objectives of this study are to:

CONFIDENTIAL

STUDY DRUG: QUIZARTINIB
PROTOCOL DATE: 10 AUGUST 2020

DEVELOPMENT INNOVATIONS STUDY NUMBER: AML 48
VERSION 4.0

- Determine the safety and tolerability of CPX-351 with quizartinib in patients with relapsed or refractory FLT3-ITD mutation-positive AML.
- Determine the overall complete morphologic (per World Health Organization) and molecular remission rate of CPX-351 and quizartinib in patients with relapsed or refractory FLT3-ITD.

2.2 Secondary Objectives

The secondary objectives of this study are to:

- Define the time to ANC and platelet count recovery
- Define the number of patients proceeding to an alloHCT
- Determine time to progressive disease (PD) or DOR
- Determine event-free survival (EFS)
- Determine OS
- Define the percentage of patients who develop late responses
- Define the number of patients who can receive consolidation and maintenance therapy on this study
- Define the treatment-related mortality rate of this combination
- Determine the percentage of patients who achieve a PR or molecular CR
- Determine the mean elapsed time for patients to achieve molecular CR
- Determine whether quizartinib is tolerable after alloHCT or DLI

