6.5.12 Minimal Residual Disease Assessment

Invivoscribe, Inc. will use an assay to determine MRD status after treatment with quizartinib and CPX-351. Minimal residual disease is defined as the minimal traceable persistence of leukemia after treatment.

The assay uses PCR amplification of exons 14 and 15 of FLT3. The PCR primers contain gene-specific regions that are coupled with NGS adaptors designed to identify ≥ 1 FLT3-ITD-containing cell in 10,000 BM cells. An MRD⁻ status will be defined as all results from BM that are negative for the presence of residual clonal cells (<1 FLT3-ITD-containing cell in 10,000 bone marrow cells). A MRD⁺ status will be defined as all results from whole blood or BM that are positive for residual clonal cells (≥ 1 FLT3-ITD-containing cell in 10,000 bone marrow cells). In addition to MRD positivity or negativity, MRD level will be monitored, and the number of residual clonal cells per 10,000 cells will be recorded as well as the total number of cells evaluated in the sample (Levis 2018b).

MRD analysis of FLT3-ITD mutations will occur with all recovery marrows with induction and consolidation cycles (if applicable) Day 35 (+/- 7 days) post-cellular therapy intervention (if applicable), as well as with bone marrow biopsies obtained during the maintenance phase. To monitor for molecular recurrence of disease, BM biopsies and aspirates will be collected at Day 24 (+/- 3 days) Cycles 3, 6, 12, and 24 during the maintenance phase.

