9. RESPONSE EVALUATIONS AND MEASUREMENTS

9.1 Complete Response (CR)

A CR will be defined as no morphologic, immunohistochemical, or flow cytometric evidence of disease by BM biopsy/aspirate and a peripheral CBC with platelet count $\geq 100,000/\mu\text{L}$ and ANC $\geq 1000/\mu\text{L}$ at the time of the bone marrow biopsy/aspirate. A molecular CR (CR_m) is defined as having no evidence of disease by BM biopsy/aspirate by morphology, immunohistochemistry, flow cytometry, and FLT3 mutation by MRD analysis. Patients with a CR but with residual MRD positivity (CR MRD⁺) are classified as indicated.

CONFIDENTIAL

STUDY DRUG: QUIZARTINIB
PROTOCOL DATE: 10 AUGUST 2020

DEVELOPMENT INNOVATIONS STUDY NUMBER: AML 48
VERSION 4.0

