10.2 Sample Size Considerations

The null hypothesis that the ORR (defined as CR + CRi) is $\leq 27\%$ (Cortes et al 2019) will be tested against a one-sided exact alternative ORR of 50% at a target significance level of 0.05. A sample size of 30 evaluable patients achieves 80% power if the true ORR is $\geq 50\%$. The null

CONFIDENTIAL

STUDY DRUG: QUIZARTINIB
PROTOCOL DATE: 10 AUGUST 2020

DEVELOPMENT INNOVATIONS STUDY NUMBER: AML 48
VERSION 4.0

hypothesis will be rejected if 13 or more responses are observed in 30 evaluable patients. In order to allow for a non-evaluable rate of 10%, a total of 34 patients will be enrolled in the study.

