10.4 Data Analysis

Descriptive statistics, including mean, median, standard deviations, and ranges for all continuous measures, will be tabulated and reported. Percentages and frequencies for all categorical measures will also be presented. Time-to-event endpoints will be reported using Kaplan-Meier estimates, with 95% CIs for median time to event.

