10.4.2 Efficacy Analysis

All efficacy analyses will be performed using the Efficacy Analysis Set.

The ORR is defined as the proportion of patients achieving a response of CR or CRi at the time of the recovery assessment. For ORR, point estimates and the associated 95% CIs (based on the Clopper-Pearson method) will be calculated.

For DOR, the estimate of the median based on Kaplan-Meier analyses will be reported. For EFS and OS, the estimated rates at 6, 12, and 24 months based on Kaplan-Meier analyses will be reported.

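### The mean time to molecular CR exists only for patients who reach it and cannot be read alone; a cumulative incidence in all treated patients would answer the objective better

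*Combined protocol and SAP*

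**What the plan says.** Section 2.2, repeated in the synopsis, asks the study to "Determine the mean elapsed time for patients to achieve molecular CR". The bullet above it is to "Determine the percentage of patients who achieve a PR or molecular CR", and Section 2.1 places the molecular remission rate within a primary objective.

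Time to molecular CR is not among the secondary endpoints in Section 2.3.2. Section 9.1 defines the status: "A molecular CR (CR_m) is defined as having no evidence of disease by BM biopsy/aspirate by morphology", and also by immunohistochemistry, flow cytometry and FLT3 MRD analysis. Section 9 does not define a time to that status. It gives no start date and no rule for patients who die, relapse or change therapy first. Elsewhere in Section 9 the start dates differ: EFS and OS run from first treatment (9.7, 9.9), but TTP runs from diagnosis of relapsed or refractory disease (9.6).

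Section 10.4 has two general rules. Continuous measures get mean, median, standard deviation and range. For the rest, "Time-to-event endpoints will be reported using Kaplan-Meier estimates, with 95% CIs for median time to event". Section 10.4.2 names only ORR, DOR, EFS and OS, for example "For DOR, the estimate of the median based on Kaplan-Meier analyses will be reported".

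On timing, Section 6.5.12 says "MRD analysis of FLT3-ITD mutations will occur with all recovery marrows with induction and consolidation cycles", at about Day 35. It adds testing after cellular therapy and at "Day 24 (+/- 3 days) Cycles 3, 6, 12, and 24 during the maintenance phase".

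**The concern.** The mean conditions on the outcome it is meant to describe. The objective names no denominator, but only achievers have an elapsed time, so no other reading gives a computable mean. Three weaknesses follow.

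- Patients lost before the first MRD marrow leave no trace in the figure.
- If death or relapse occurs between later marrows, the patients removed are those who would have responded late, so the average over the rest gets shorter. A worse course can then look like a faster response.
- The visits become widely spaced in maintenance, so the mean depends heavily on one or two late first-negative marrows.

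Section 1.4 ties survival in AML to achieving a molecular CR. The timing figure is therefore likely to be read as evidence of activity.

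**Working it through.** **The plan's own figures.** The documents give no figure for time to molecular CR. The primary design, a "one-sided exact alternative ORR of 50% at a target significance level of 0.05" against a null of 27%, reproduces. With 30 evaluable patients and rejection at 13 or more responses, exact alpha is 0.0395 and power is 0.819; 30/(1 − 0.10) = 33.3, rounded up to 34. None of this uses the time to molecular CR.

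**Check 1: constant hazards (assumed).** Let λ be the daily hazard of molecular CR, μ that of prior death or relapse, h = λ + μ, and T = 180 days.

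- Proportion achieving = (λ/h)(1 − e^(−hT))
- Mean among achievers = 1/h − T·e^(−hT)/(1 − e^(−hT))
- One minus Kaplan-Meier, losses censored = 1 − e^(−λT)

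With λ = 0.004:

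- μ = 0.002: proportion (0.004/0.006)(1 − e^(−1.08)) = 0.440; mean 166.7 − 180(0.3396/0.6604) = 74.1 days.
- μ = 0.006: proportion (0.004/0.010)(1 − e^(−1.8)) = 0.334; mean 100 − 180(0.1653/0.8347) = 64.4 days.
- One minus Kaplan-Meier is 1 − e^(−0.72) = 0.513 in both.

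**Check 2: the protocol's MRD visits.** Assume MRD marrows at about Days 35, 77 and 119 and maintenance starting near Day 130. Day 24 of Cycles 3, 6, 12 and 24 then falls on Days 210, 294, 462 and 798. Assume chances of first molecular CR at successive visits, given none before, of 0.20, 0.15, 0.15, 0.10, 0.10, 0.10 and 0.05. Without losses, the probability p of first reaching it at each visit is 0.200, 0.120, 0.102, 0.0578, 0.0520, 0.0468 and 0.0211. These sum to 0.600, and the mean is Σ(p × day)/Σp = 94.25/0.5997 = 157 days. With a constant hazard of prior loss equal to ln 2/median, each p is multiplied by e^(−hazard × day):

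| Median time to prior death or relapse | Proportion achieving | Mean among achievers |
|---|---|---|
| No losses | 60% | 157 days |
| 730 days | 52% | 133 days |
| 365 days | 46% | 116 days |
| 180 days | 38% | 93 days |
| 90 days | 28% | 72 days |

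With responses assumed to come earlier (0.30, 0.10, 0.10, 0.05, 0.05, 0.05, 0.02), the mean falls from 109 to 54 days as the proportion falls from 52% to 30%.

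**Check 3: losses only before the first MRD marrow.** Under the first set of rates, losing 10% or 30% of patients before Day 35 multiplies every p by 0.9 or 0.7. The proportion falls from 60% to 54% or 42%, and the mean stays at 157 days.

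**Check 4: one late marrow.** Day 24 of Cycle 24 is 23 × 28 + 24 = 668 days into maintenance. If nine achievers are first negative at Day 35 and one at that marrow, the mean is at least (9 × 35 + 668)/10 = 98 days, while the median is 35. In the no-loss row of Check 2, the last visit holds 0.0211/0.5997 = 3.5% of achievers; without it the mean is 77.44/0.5786 = 134 days instead of 157.

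**The case against.** The strongest reply is that this is one descriptive item among eleven secondary objectives. It carries no test, threshold or decision, and the proportion is reported beside it. That stands: a reader might infer that the trial never shows how many patients reach molecular remission, and Sections 2.1 and 2.2 show otherwise. The secondary bullet pools molecular CR with PR, but the primary objective covers the molecular remission rate.

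A second reply is that Section 10.4 already provides median, standard deviation and range with the mean for continuous measures. That also stands, and it eases the sensitivity to a late marrow. All of those statistics are still taken over achievers only.

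A reader might go further and infer that the plan prescribes Kaplan-Meier with deaths and relapses censored, which would overstate achievement (0.513 against 0.440 or 0.334 in Check 1). The documents do not say so. The general Kaplan-Meier sentence is not tied to this objective, Section 10.4.2 does not name it, and a Kaplan-Meier median is not the mean requested. The fair statement is that the method is unsettled.

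The sizes are also open to challenge. If Check 1's hazards are applied to MRD visits at Days 35, 77 and 119, with detection at the next visit while event-free, the mean moves only from 73 to 68 days; adding Day 210 gives 111 to 94. With 30 evaluable patients, Check 1 implies about 10 to 13 achievers and a standard error near 14 to 15 days on each mean, so its 10-day shift would lie within noise.

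**Conclusion.** The point holds as a minor improvement. The mean time to molecular CR is conditional on achieving it and should not be read alone. It is blind to losses before the first MRD marrow, can shorten when later losses remove late achievers, and is sensitive to single late marrows.

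The hazards, visit probabilities and maintenance start date are all assumed, because the documents give none. Only the direction is established. It would be too strong to say that the mean always shortens as more patients die or relapse: Check 3 shows it unchanged when the losses come early. It would also be too strong to say that the trial's efficacy conclusion is affected, since the primary ORR test and sample size do not use this figure.

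**What to change.** Replace the mean with the cumulative incidence of first molecular CR:

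- Measure from first dose of study treatment, in all treated patients, to the first marrow meeting the Section 9.1 definition.
- Treat death, relapse or progression, and start of non-protocol anti-leukaemic therapy as competing events.
- Report the estimate with confidence intervals at the scheduled MRD marrows.
- Do not make protocol-permitted cellular therapy a competing event in the main estimate. MRD testing is scheduled after it (Sections 6.4.3 and 6.5.12, Appendix D), and those results would be discarded. Show molecular CR first reached after cellular therapy separately or in a sensitivity analysis.
- Give the median and range among achievers for description only.
- State in Section 10.4.2 that this method, not the general Kaplan-Meier rule, applies to the item.

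The cost is a few lines of text and one standard competing-risks estimate from data already collected. Intervals will be wide with about 34 patients. No visits, samples or patients are added.

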2.3 Endpoints

2.3.1 Primary Endpoints

- Response rate determination:
 - Complete remission (CR) defined as a complete morphologic response with complete blood count recovery ANC $\geq 1000/\mu\text{L}$ and platelet count $\geq 100,000/\mu\text{L}$, per the revised International Working Group response criteria (Cheson et al 2003).
 - Complete remission with minimal residual disease (CR with MRD): Achievement of a complete morphologic CR with persistent disease detected by flow or molecular MRD analysis.
 - A complete morphologic response with an incomplete blood count recovery ([CRi] ANC $< 1000/\mu\text{L}$ and/or platelet count $< 100,000/\mu\text{L}$), per the revised International Working Group response criteria (Cheson et al 2003). Patients will be further divided into MRD⁺ and MRD⁻ subgroups.

CONFIDENTIAL

STUDY DRUG: QUIZARTINIB
 PROTOCOL DATE: 10 AUGUST 2020

DEVELOPMENT INNOVATIONS STUDY NUMBER: AML 48
 VERSION 4.0

- A partial response (PR) is defined as having persistence of disease, with a $\geq 50\%$ decrease in the blast percentage with or without the presence of FLT3-ITD mutations.

2.3.2 Secondary Endpoints

- Time to ANC recovery >56 days ($\geq 500/\mu\text{L}$) and platelet count recovery >56 days ($\geq 50,000/\mu\text{L}$)
- Number of patients proceeding to an alloHCT
- Time to PD or DOR
- EFS
- OS

3. STUDY PATIENT POPULATION AND DISCONTINUATION

3.1 Inclusion Criteria

Patients must meet all of the following criteria in order to be included in this research study:

1. Written informed consent form (ICF), according to local guidelines, signed by the patient or by a legal guardian prior to the performance of any study-related screening procedures
2. Male and female patients between ≥ 18 and < 80 years old
3. Patients with the following types of AML with $> 5\%$ blasts:
 - Relapsed FLT3-ITD mutation-positive AML, diagnosed by bone marrow (BM) biopsy with FLT3 mutation by polymerase chain reaction (PCR)
 - Refractory FLT3-ITD mutation-positive AML, diagnosed by BM biopsy with FLT3 mutation by PCR
 - Relapsed or refractory FLT3-ITD mutation-positive AML after HCT, diagnosed by BM biopsy with FLT3 mutation by PCR
 - Relapsed or refractory AML with de novo FLT3-ITD mutation, diagnosed by BM biopsy with FLT3 mutation by PCR
 - Relapsed or refractory AML after HCT with de novo FLT3-ITD mutation, diagnosed by BM biopsy with FLT3 mutation by PCR
4. First-line therapy must have contained a standard induction chemotherapy (e.g., 7+3, FLAG-IDA, FLAG, CLAG, MEC, hypomethylating agent with venetoclax) with or without receiving a prior FLT3 inhibitor (e.g., midostaurin) or multi-tyrosine kinase inhibitor (e.g., sorafenib). All patients who relapsed after an alloHCT are included, except patients with active graft-versus-host disease (GVHD) requiring > 10 mg prednisone.
5. Patients must be able to swallow and retain oral medication.

CONFIDENTIAL

STUDY DRUG: QUIZARTINIB
 PROTOCOL DATE: 10 AUGUST 2020

DEVELOPMENT INNOVATIONS STUDY NUMBER: AML 48
 VERSION 4.0

6. Eastern Cooperative Oncology Group (ECOG) Performance Status score of 0, 1, or 2 (Appendix A)
7. Adequate renal and hepatic parameters (aspartate aminotransferase [AST], alanine aminotransferase [ALT] ≤ 2.5 institutional upper limit of normal [ULN]; total bilirubin ≤ 2.0 institutional ULN; serum creatinine [Cr] ≤ 2.0). In patients with suspected liver infiltration, ALT can be ≤ 5 institutional ULN.

3.2 Exclusion Criteria

Patients who meet any of the following criteria will be excluded from study entry:

1. Acute promyelocytic leukemia (t[15;17])
2. Female patients who are lactating or have a positive serum pregnancy test during the screening period. Female patients of childbearing potential who are not willing to employ highly effective birth control (as defined in Appendix C) from screening to 6 months following the last dose of CPX-351 and/or quizartinib.
3. Fertile male patients, defined as all males physiologically capable of conceiving offspring, with female partners of childbearing potential must use condoms plus a spermicidal agent during the study treatment period and for 6 months following their last dose of CPX-351 and/or quizartinib, and must not father a child during this period.(refer to Appendix C)
4. Evidence of active and uncontrolled bacterial, fungal, parasitic, or viral infection. Infections are considered controlled if appropriate therapy has been instituted and, at the time of screening, no signs of active infection progression are present. This is assessed by the site clinicians, including an infectious disease consulting physician, if requested by the Principal Investigator (PI), regarding adequacy of therapy. These infections include, but are not limited to:
 - Known human immunodeficiency virus (HIV) infection
 - Active hepatitis B or C infection with rising transaminase values
 - Active tuberculosis infection
5. History of hypersensitivity to cytarabine, daunorubicin, or an FLT3 inhibitor
6. Any patients with known significant impairment in gastrointestinal (GI) function or GI disease that may significantly alter the absorption of quizartinib
7. Psychological, familial, sociological, or geographical conditions that do not permit compliance with the protocol
8. Uncontrolled or significant cardiovascular disease, including any of the following:
 - Bradycardia of less than 50 beats per minute, unless the patient has a pacemaker
 - QTcF interval using Fridericia's correction factor (QTcF) interval prolongation, defined as >450 msec at screening and prior to first administration of quizartinib.

CONFIDENTIAL

STUDY DRUG: QUIZARTINIB
 PROTOCOL DATE: 10 AUGUST 2020

DEVELOPMENT INNOVATIONS STUDY NUMBER: AML 48
 VERSION 4.0

- Diagnosis of or suspicion of long QT syndrome (including family history of long QT syndrome)
 - Systolic blood pressure ≥ 180 mmHg or diastolic blood pressure ≥ 110 mmHg
 - History of clinically relevant ventricular arrhythmias (i.e., ventricular tachycardia, ventricular fibrillation or Torsades de pointes)
 - History of second or third degree heart block without a pacemaker
 - Right bundle branch and left anterior hemiblock (bifascicular block), complete left bundle branch block
 - Ejection fraction $< 50\%$ by transthoracic echocardiogram (TTE) or multigated acquisition (MUGA) scan
 - History of uncontrolled angina pectoris or myocardial infarction within 6 months prior to Screening
9. History of New York Heart Association Class 3 or 4 heart failure (Appendix B)
 10. Prior anthracycline (or equivalent) cumulative exposure ≥ 368 mg/m² daunorubicin (or equivalent)
 11. Any serious underlying medical condition that, in the opinion of the Investigator or Medical Monitor, would impair the ability to receive or tolerate the planned treatment.
 12. Patients with inadequate pulmonary function will be excluded. Inadequate pulmonary function is defined as requiring supplemental O₂ or diffusing capacity of the lungs for carbon monoxide [DLCO] $< 40\%$.
 13. Active acute or chronic GVHD requiring prednisone > 10 mg or equivalent.

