Study Drug, Dose, and Mode of Administration:	
Induction phase: CPX-351 (daunorubicin 44 mg/m² IV and cytarabine 100 mg/m² IV) will be given on Days 1, 3, and 5 followed by 30 mg quizartinib by mouth (PO) once daily on Days 8-21. Patients with an incomplete response, but a >50% reduction in the blast count/cellularity ratio compared to the most recent bone marrow (BM) biopsy prior to treatment, should receive one additional cycle of induction therapy (re-induction) with CPX-351 (daunorubicin 44 mg/m² IV and cytarabine 100 mg/m² IV) on Days 1 and 3 only. Re-induction will begin after a 72-hour washout period from the last dose of quizartinib. During re-induction, treatment with quizartinib will resume on Day 6 and continue through Day 21. Any patient with neutropenia or thrombocytopenia lasting ≥ 56 days from the initiation of CPX-351 will not receive consolidation and will instead proceed to the maintenance phase.
 
Consolidation phase: At the Investigator's discretion, patients who achieve CR and do not proceed to an alloHCT or other CT intervention will proceed to the consolidation phase beginning 7 days (± 7) after neutrophil recovery (ANC >1000/μL). Administer up to 2 consolidation cycles of CPX-351 (daunorubicin 29 mg/m² IV and cytarabine 65 mg/m² IV) on Days 1 and 3. Begin quizartinib 30 mg PO once daily on Days 6-21.
 
Maintenance phase: Maintenance dosing of quizartinib will begin at 30 mg/day on Days 1-14, and if there are no non-hematologic Grade ≥ 3 toxicities, the quizartinib dose will increase to 60 mg/day on Day 15. The maintenance phase is a 28-day cycle beginning 7 days (± 7) after neutrophil recovery (ANC >1000/μL) from the consolidation phase or induction phase. Patients will receive quizartinib once daily for a total of 24 cycles or until disease relapse

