3.3 Discontinuation from Study Treatment

Patients will be discontinued from study treatment for any of the following reasons:

- Irreversible or intolerable toxicity or abnormal laboratory values thought to be related to drug toxicity
- Conditions requiring therapeutic intervention not permitted by the protocol
- Intercurrent illness (this will be at the Investigator's discretion)
- Inability of the patient to comply with study requirements
- Patient requests to discontinue treatment, but agrees to finish study procedures
- Patient withdraws consent from the study and is discontinued from the study
- Non-compliance/lost to follow-up
- Pregnancy and breastfeeding
- Further participation would be injurious to the patient's health or well-being, in the Investigator's medical judgment

CONFIDENTIAL

STUDY DRUG: QUIZARTINIB
 PROTOCOL DATE: 10 AUGUST 2020

DEVELOPMENT INNOVATIONS STUDY NUMBER: AML 48
 VERSION 4.0

- The study is terminated by the Sponsor, Sarah Cannon Development Innovations (“Development Innovations”) or the Institutional Review Board (IRB)

After discontinuation from protocol treatment, patients must be followed for adverse events (AEs) for 30 days after their last dose of study drug. All new AEs occurring during this period must be reported and followed at the site until resolution for AEs attributed to the study medication(s).

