5.2.3 Consolidation Phase

Patients who achieve a CR and do not proceed to an alloHCT or other CT intervention will proceed from induction to the consolidation phase beginning 7 days (± 7 days) after neutrophil recovery (ANC $> 1000/\mu\text{L}$), receiving up to 2 consolidation cycles consisting of CPX-351 (daunorubicin 29 mg/m² IV and cytarabine 65 mg/m² IV) on Days 1 and 3. Quizartinib therapy (30 mg PO once daily) will start on Day 6 and continue through Day 21.

After the first consolidation cycle, if it is believed by the PI and/or sub-investigator that a patient with prolonged Grade ≥ 3 toxicity would have additional adverse toxicities during the second consolidation phase, and/or there is CRi with persistent ANC $< 1000/\mu\text{L}$ and/or platelets $< 50,000/\mu\text{L}$ more than 14 days from the recovery marrow assessment, then the patient could proceed to a cellular intervention or the maintenance phase.

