7.5.2 Precautions and Risks Associated with CPX-351

- Cardiotoxicity

The total cumulative dose of non-liposomal daunorubicin >550 mg/m² has been associated with an increased incidence of drug-induced congestive heart failure. In patients who received radiation therapy, the maximum tolerable lifetime dose is 400 mg/m². Calculate maximum lifetime exposure prior to each cycle as shown in Table 1.

Table 1 Cumulative Exposure of Daunorubicin per Cycle of CPX-351

Therapy	Daunorubicin per Dose	Number of Doses per Cycle	Daunorubicin per Cycle
First induction cycle	44 mg/m ²	3	132 mg/m ²
Second induction cycle	44 mg/m ²	2	88 mg/m ²
Each consolidation cycle	29 mg/m ²	2	58 mg/m ²

CONFIDENTIAL

See dose modification/administration guidelines (Appendix G).

- Hemorrhage

12% Grade ≥ 3 (8% in control/7+3 arm), fatal non-disease associated CNS hemorrhage 2% (0.7% in control arm)

- Hypersensitivity

Known in patients receiving cytarabine and daunorubicin. See dose modification/administration guidelines (Appendix G).

- Tissue necrosis

Administer by central venous catheter

- Embryo-fetal toxicity

Counsel to avoid pregnancy, and to use contraception through 6 months after last administration of agent. Because of the potential for serious adverse reactions in breastfed infants, advise lactating women not to breastfeed during treatment with CPX-351. In males, CPX-351 may cause infertility. In male patients wishing to conceive in the future, cryopreservation of sperm prior to administration is recommended.

- Cytopenias

Prolonged thrombocytopenia (<50 beyond Day 42) 28% (versus 12%) in induction and 25% (versus 16%) in consolidation; prolonged neutropenia (ANC <500 beyond Day 42) 17% (versus 3%) in induction and 10% (versus 3%) in consolidation. See dose modification/administration guidelines (Appendix G).

- Chemistry abnormalities

Hyponatremia (14%, 6% with consolidation), hypokalemia (9%, 6% with consolidation), hypoalbuminemia (7%, 2% with consolidation), hyperbilirubinemia (6%, 2% with consolidation), and elevated ALT (5%, 0% with consolidation); all were similar in comparison to 7+3.

The most common serious adverse reactions (incidence $\geq 5\%$) were dyspnea, myocardial toxicity, sepsis, pneumonia, febrile neutropenia, bacteremia and hemorrhage. Adverse reactions led to discontinuation of CPX-351 in 18% of patients (13% in the control arm).

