Appendix G Management of CPX-351-Related Adverse Events

NCI CTCAE Grade	CPX-351 Action
Cardiotoxicity	Discontinue CPX-351 immediately without resumption
Hypersensitivity Grade 1	Once symptoms resolve, reinitiate infusion at half the prior rate of infusion. Consider premedication with antihistamines and/or corticosteroids for subsequent doses.
Hypersensitivity Grade 2	Do not reinitiate infusion. For subsequent doses, pre-medicate with antihistamines and/or corticosteroids prior to initiating infusion at same rate.
Hypersensitivity Grade ¾	Permanently discontinue treatment, treat according to the standard of care to manage symptoms, and monitor patient until symptoms resolve.
Neutropenia lasting ≥56 days	Proceed to maintenance therapy with quizartinib
Thrombocytopenia lasting ≥56 days	Proceed to maintenance therapy with quizartinib

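### Exclusion criterion 10 admits previously irradiated patients whose first induction would exceed the 400 mg/m² lifetime maximum in Section 7.5.2, and no dose-based action is attached to the required pre-cycle calculation

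*Combined protocol and SAP*

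**What the plan says.** Criterion 10 (Section 3.2, repeated in the synopsis) is a single limit on "Prior anthracycline (or equivalent) cumulative exposure": 368 mg/m² daunorubicin equivalent or more excludes. It makes no adjustment for radiation. Prior radiotherapy is recorded under Section 6.5.1 but is not an exclusion, and Section 3.1 includes patients who relapsed after alloHCT.

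Section 7.5.2, under cardiotoxicity, makes three statements:

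- A cumulative dose of non-liposomal daunorubicin above 550 mg/m² is associated with more heart failure.
- A lower figure, in mg/m², is given after radiation: "In patients who received radiation therapy, the maximum tolerable lifetime dose is 400".
- Sites must work out the running total every time: "Calculate maximum lifetime exposure prior to each cycle as shown in Table 1".

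The table referred to lists the daunorubicin content of each CPX-351 cycle, and the reader is then sent to Appendix G. The cardiac row there is triggered by observed cardiotoxicity: "Discontinue CPX-351 immediately without resumption". The other rows cover hypersensitivity and cytopenias lasting 56 days or more.

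Section 8.3.1, on CPX-351 dose interruptions and adjustments, deals only with how long adverse events last. Section 3.3 lists no cumulative-dose reason for stopping. Section 1.5 says that patients whose cumulative anthracycline dose exceeds 550 mg/m² will be excluded, which does not match the 368 in criterion 10 and does not mention radiation.

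**The concern.** For irradiated patients, the eligibility rule and the dose maximum cannot both be followed across part of the eligible range, and the clash comes in the first cycle. If the 400 figure is advisory, the mandatory calculation decides nothing. If it is an implied stop, criterion 10 enrols patients who cannot receive the full planned induction, and some who cannot receive any of it.

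One site could dose past 400 while another withholds doses or the whole cycle, and no rule would settle which is right. At stake are the cardiac safety of a small subgroup and consistent delivery of the regimen whose safety and response rate the trial is meant to measure.

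**Working it through.** **Inputs.** Criterion 10: excluded at 368 mg/m² or more. Section 7.5.2: 400 mg/m² after radiation, and 550 mg/m² as the general figure. Table 1: 44 mg/m² × 3 doses (first induction), 44 × 2 (second induction), 29 × 2 (each consolidation, at most two).

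**Reproducing Table 1.** 44 × 3 = 132; 44 × 2 = 88; 29 × 2 = 58 mg/m². All three agree with the protocol.

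**First induction against 400.** The highest prior exposure that stays within the limit is 400 − 132 = 268. Patients above 268 and below 368 are eligible and would pass 400. At the top of the range the total is just under 368 + 132 = 500, an excess of just under 100 mg/m².

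**If 400 is read as a stop,** the number of the three 44 mg/m² induction doses that fit depends on prior exposure:

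- All three fit up to 400 − 132 = 268.
- Two fit up to 400 − 88 = 312.
- One fits up to 400 − 44 = 356.
- None fits above 356. At 367, for example, only 400 − 367 = 33 mg/m² remains.

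**Later cycles.** Highest prior exposure that stays within each figure (limit minus planned on-study dose, mg/m²):

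| Cycles received | On-study dose | Within 400 | Within 550 |
|---|---|---|---|
| First induction | 132 | 268 | 418 |
| + 1 consolidation | 132 + 58 = 190 | 210 | 360 |
| + re-induction | 132 + 88 = 220 | 180 | 330 |
| + 2 consolidations | 132 + 116 = 248 | 152 | 302 |
| + re-induction, 1 consolidation | 132 + 88 + 58 = 278 | 122 | 272 |
| Full course | 132 + 88 + 116 = 336 | 64 | 214 |

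Without radiation, first induction cannot reach 550: the 418 in the table lies above the 368 entry limit. Only the conditional later cycles can pass it.

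**The case against.** The strongest reply is that both figures sit in a precautions section, not in the eligibility or dose-modification rules, and that 550 is given for non-liposomal daunorubicin as an association. The 400 sentence follows directly, so the same caveat may apply to it. This stands as a limit on the strength of the evidence: the documents do not show that either figure is right for CPX-351. It does not remove the conflict, because the protocol itself calls 400 a maximum and lists CPX-351's daunorubicin in Table 1 for that calculation.

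It can also be said that placing a maximum beside an instruction to calculate already implies a stop, and that the Section 1.5 sentence may be meant for on-study dose. The implied stop is a fair reading, but criterion 10 then admits patients who cannot receive the cycle. Section 1.5 reads most naturally as an entry rule, and on either reading it does not address 400.

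Other safeguards exist:

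- Criterion 8 excludes an ejection fraction below 50%, and criterion 9 excludes a history of NYHA Class 3 or 4 heart failure.
- Criterion 11 covers serious underlying conditions that "would impair the ability to receive or tolerate the planned treatment".
- Section 3.3 allows discontinuation where "Further participation would be injurious to the patient".
- Consolidation is flexible, with patients "receiving up to 2 consolidation cycles consisting of CPX-351".
- Appendix G stops CPX-351 once cardiotoxicity appears.

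These reduce the consequence, but none is a cumulative-dose rule. The pre-consolidation TTE or MUGA in Section 6.5.4 is a weak support, because Appendix D schedules that test at screening only. Section 7.3.2 refers sites to the IB and USPI. Whether those give an action cannot be checked here, and they would not alter criterion 10.

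A reader might infer that 550 should also be a mandatory cap for everyone. The documents do not support that. Section 7.5.2 does not call 550 a maximum, first induction cannot reach it in an eligible patient, and withholding re-induction or consolidation on that basis is a clinical trade-off in a population with few options.

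**Conclusion.** The point holds for previously irradiated patients. Criterion 10 leaves a window of prior exposure, above 268 and below 368 mg/m², in which the planned first induction takes an eligible patient past the protocol's stated 400 mg/m² maximum, by up to just under 100 mg/m². Below that window, an irradiated patient can still pass 400 in later cycles, from a prior exposure above 64 mg/m² if the full course is given. In neither case do the documents say what the required calculation decides.

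This rests on counting CPX-351 daunorubicin milligram for milligram, as Table 1 does, and on taking radiation therapy without qualification of site or dose, as Section 7.5.2 does. How many of the approximately 34 patients fall in the window cannot be estimated. Nothing here shows that 400 is the correct limit for the liposomal product or that patients would be harmed; the finding is that the protocol should act on the limit it states.

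**What to change.** 1. **Criterion 10 and synopsis.** Add that patients with prior radiation therapy, as defined by the clinical team, are excluded if prior exposure is above 268 mg/m² daunorubicin equivalent (400 − 132). The documents give no basis for the definition (site, dose), so clinicians must write it and confirm the value.

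2. **Section 7.5.2 and Appendix G.** State that before each CPX-351 cycle, including first induction, the Table 1 dose is added to all anthracycline received to date, and that a patient with prior radiation does not receive the cycle if the total would exceed 400 mg/m². A patient in CR or CRi then goes to cellular therapy or quizartinib maintenance. That route exists in Sections 5.2.2 and 5.2.3, but its triggers there are prolonged toxicity or cytopenia, so this would be a new trigger. The clinical team sets the route for a patient in PR; Section 5.2 already allows cellular therapy followed by maintenance in PR where indicated.

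3. **Section 1.5.** Align the 550 exclusion sentence with criterion 10, and let the clinical team decide whether 550 is also a per-cycle stop for non-irradiated patients.

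**Cost.** A protocol amendment that changes eligibility and needs IRB approval. Section 6.5.1 records prior radiotherapy but does not name site or dose, so the case report form may need explicit fields. A few irradiated patients, possibly including relapses after alloHCT, may become ineligible or lose later CPX-351 cycles; a patient entering at exactly 268 would reach 400 on first induction and receive no further CPX-351.
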